**Description of Study Visits:**

Subjects will meet with a member of the study team for 8-11 study visits, during regular dialysis treatments at their outpatient clinics. Study activities for each of the study visits are described below. In addition to the study visits, subjects will continue their regularly scheduled dialysis treatments and must receive at least half of the treatments at their outpatient clinic (6 out of 12 scheduled) for each treatment period and the 30-day Baseline Observation Period. \*Procedures for missed treatments for each period are described below. Adverse events will be collected from the date of consent until study visit #11. For subjects who elect to keep the ILR LINQ device implanted at the end of the last treatment, adverse events and severe adverse events will be collected until a week after study visit #9.

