### **Study A Intervention - Dialysate K/HCO3 Trial: Monthly Visits:**

Study treatment to be started on the 1st Monday/Tuesday following the Week 4 Reveal Visit. There will be 4 crossover groups and subjects will rotate monthly through all the treatment groups in a random blinded order. Prior to initiation of all HD sessions, subjects will receive POC testing via the Abbott i-STAT, which requires approximately 100uL of blood. This testing, along with their treatment arm assignment, will drive the dialysate prescription for that specific HD session (see figures/tables further below). The 4 cross-over groups are listed below:

- i. Potassium Removal Maximization strategy, 1 month (low dialysate K)
- ii. Potassium Gradient-Minimization Strategy, 1 month (high dialysate K)
- iii. Acidosis Avoidance, 1 month (low dialysate bicarbonate)
- iv. Alkalosis Avoidance, 1 month (high dialysate bicarbonate)

There will be a 1-week washout period between subsequent interventions and during this week, participants' dialysate prescription will be determined by their dialysis physician. Dialysis treatment records will be reviewed at least monthly and standard of care labs will be recorded at visits 5 through 8.

Subjects enrolled in the optional substudy will press the button on the REVEAL patient assistant device to automatically trigger their implanted REVEAL LINQ ILR to record an EKG tracing each time their blood drawn is drawn by the dialysis staff prior to dialysis for POC testing. Subjects will also record a full transmission upon returning home from dialysis with the Carelink Transmitter.

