**Adherence Endpoints**—Adherence will be assessed for each of the 4 dialysate interventions (K removal minimization vs. maximization, acidosis vs. alkalosis avoidance) as the % of sessions in which POC testing is completed and the dialysate is adjusted according to the algorithm. For the UF trial, it will be assessed as the % of sessions in which the mandated UF rate is delivered. We hypothesize that 90% adherence is achievable. HD staff will be anonymously surveyed once 3 subjects have completed 1 month of each trial and once 6 patients have completed each trial. A questionnaire will identify the impact of time constraints, patient refusal, algorithm complexity, inadequate training on POC devices, clinical concerns, or other factors on protocol adherence. Face-to-face review with HD staff will facilitate identification of other barriers. Where addressable factors are identified, they will be corrected for remainder of the trials. Since the overall goal is to assess implementation feasibility, secondary analyses will compare pre- and post-correction adherence in addition to estimating overall adherence. This adaptive plan will facilitate identification of best practices and ensures that estimates represent the feasibility of subsequent protocols to be implemented after incorporating lessons learned in the pilot experience.

**Secondary Feasibility Measures**—POC electrolyte measurements will be compared with usual care monthly labs to assess accuracy of POC testing. An additional metric that will be used to determine the impact of POC testing on trial design will be the percent of sessions in which the POC-guided dialysate prescription differs from a hypothetical prescription in which the choice of dialysate is based solely on the once-monthly lab.

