**Safety** will be assessed by calculating the incidence rate (complications per unit follow-up time) for serious adverse events and intervention-specific complications. Comparisons of incidence rate between interventions will utilize Poisson regression adjusted for randomization scheme and site. Exploratory analyses will assess age, sex, race, mean intra-dialytic weight gain, potassium concentration and HCO3 concentration in month prior to randomization on the incidence of adverse events. Given the pilot nature of the trials and major goal of informing feasibility estimates for definitive trials, P<0.05 will be considered significant in all safety analyses. No adjustments will be made for multiple comparisons given the pilot nature of the studies.

**Efficacy** estimates for Aim 3 will utilize the mean duration of CSA as the primary outcome. In the event of incomplete follow-up, this will be indexed to duration of follow-up time (e.g. minutes per day). Change in CSA duration between interventions will be analyzed using mixed effects linear regression with terms for treatment, research site, period, sequence, and random effects for subjects. Primary outcomes for the dialysate trial will compare CSA during potassium maximization vs. minimization, and acidosis vs. alkalosis avoidance. For the UF trial, aggressive vs. conservative UF will be compared. Physiologically, the washout period of 1-week in the dialysate trial and 1 weekend in the UF trial is sufficient to avoid the possibility of carryover effects. Potential for sequence effects is minimized by a design with uniform sequences (all treatments appear once within each sequence). Potential for carryover and randomization sequence effects will be analyzed by including terms for sequence and their interaction with treatment in the models.

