**i. Phlebotomy:** Momentary discomfort as well as bruising may occur during routine phlebotomy. To eliminate this risk, we will obtain blood through the patients' vascular access while they are receiving dialysis, and there will be no access of the dialysis access or venipuncture purely for study purposes. We plan to use the minimal amount of blood necessary for POC testing, which is  $<1$  mL (100  $\mu$ L). The total amount of blood required for testing over 5 months will be approximately 52 mL. This is unlikely to cause a significant change in blood counts or symptomatic anemia, and the risks associated with this degree of blood loss can be considered minimal. Risk will be further minimized by putting the protocol on hold for subjects with severe anemia (defined as hemoglobin  $<8$  mg/dL) on the most recent (monthly) standard of care labs and resuming only when anemia resolves.

**ii. ILR insertion:** ILR insertion requires administration of local anesthesia or conscious sedation and a small subcutaneous puncture for device placement. Risks of local anesthesia are minimal but could include very rare allergic reactions to subcutaneous anesthetic agents (subjects will be screened for anesthetic allergy). Transient bruising and discomfort is expected and will be treated as needed with over the counter agents. Prior investigator experience with ILR devices suggest that more significant complications such as discomfort requiring explanation and bacteremia are very rare. Local infection may occur. Prior experience suggests that even in the dialysis population these are typically mild infections which are treatable with oral antibiotics and do not require device removal. These risks will be disclosed to subjects. Subjects with conditions that place them at high risk of infection (e.g. severe psoriasis, multiple prior infections, immunosuppression) will be excluded to further minimize risks. Finally, subjects will be assessed within 1 week after device implantation and at 1 month to assess for proper wound healing and to allow early identification and treatment of infections.

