Study procedures ensure testing of electrolytes at each session (3x/week) in contrast to a frequency of as little as 1x/month in routine practice. Severe electrolyte abnormalities will thus be recognized earlier with study patients than in routine practice. Similarly, POC testing will ensure that the dialysis prescription will be adjusted according to the ambient potassium or bicarbonate at that dialysis session. In routine practice, follow-up testing at outpatient dialysis units typically has a turn-around time of hours (stat testing) or days (routine lab draws) which makes appropriate adjustment of the dialysis prescription unfeasible. Thus, study procedures may actually lower the risk of severe electrolyte abnormalities or risk of complications from those abnormalities. However, significant inaccuracy in the point of care testing results could modify the associated risks.

To further mitigate risk, patients with severe abnormalities in potassium ( $K>6.5$  or  $<3.0$ ) or bicarbonate ( $<20$  or  $>32$ ) will temporarily come off therapy and be treated off-protocol at the discretion of their clinician.

**Study B UF algorithms** are designed to either limit UF rates to  $\leq 10$  mL/kg/hour or to allow UF rates  $\geq 13$  mL/kg/hour. As discussed in the research summary, there is significant equipoise regarding the risk/benefit ratio of either strategy, as the use of high UF rates minimizes the risk of volume overload at the expense of rapid fluid shifts, whereas limiting UF rate minimizes the risk of rapid fluid shifts at the expense of increasing the risk of volume overload. Both strategies are routinely employed in clinical care. Thus, it is again unclear whether research-related risks are materially different than those in routine practice. As described in the Research Plan, subjects will cross over weekly between the unlimited and restricted UF treatments, thereby allowing removal of excess fluid accumulated during the restrictive week during the subsequent, unlimited week. This will limit any excessive fluid gains to a maximum of a few liters over the course of the restricted UF week thereby limiting the possibility of volume-related complications in the event patients fail to self-regulate intake of salt and water. Safety, will be further ensured because patients who show signs of significant volume overload will have the

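### Study A's severe potassium and bicarbonate rate falls as testing completeness falls, because a test-dependent event is divided by undefined follow-up time

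*Combined protocol and SAP*

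**What the plan says.** In section VI, the Safety paragraph under Statistics and Analysis assesses safety by "calculating the incidence rate (complications per unit follow-up time) for serious adverse events and intervention-specific complications". It adds that "Comparisons of incidence rate between interventions will utilize Poisson regression adjusted for randomization scheme and site" and that "P<0.05 will be considered significant in all safety analyses". Follow-up time is not defined and no offset is named. The Statistical Methodology entry of the Study Summary repeats the approach without giving a denominator.

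Safety Endpoints, in the same section, puts severe laboratory values among the Study A complications: potassium at or above 6.5 or at or below 3.0 mEq/L, and bicarbonate below 20 or above 32 mEq/L. It does not say which measurements count.

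The other relevant places are:

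- **Testing.** Section V (Study A, Monthly Visits) says: "Prior to initiation of all HD sessions, subjects will receive POC testing via the Abbott i-STAT". Standard-of-care labs, whose panel includes potassium and bicarbonate, are also recorded at visits 5 to 8.
- **Attendance.** Under Description of Study Visits, subjects "must receive at least half of the treatments at their outpatient clinic (6 out of 12 scheduled) for each treatment period". A period is extended only after 7 or more missed sessions.
- **Completeness.** Adherence Endpoints counts a session as adherent only if the POC test was done and the dialysate adjusted. It states "We hypothesize that 90% adherence is achievable". Aim 1 in section II hypothesises at least 80%.
- **Holds.** Section VII describes "putting the protocol on hold for subjects with severe anemia". It also says that patients with severe potassium or bicarbonate values "will temporarily come off therapy and be treated off-protocol at the discretion of their clinician". Neither hold has a stated duration.

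**The concern.** A hospitalization or an unscheduled dialysis comes to light whether or not anyone took a sample, so person-time is a sound denominator for it. A severe potassium or bicarbonate value exists only if blood was tested. For that component, time at risk and opportunity to detect are different quantities, and the plan uses the first without linking it to the second.

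Aim 1 asks whether severe potassium and bicarbonate abnormalities will be minimal, in a pilot where completion of POC testing is itself under study. With a time denominator, a failure to test appears as a lower severe-value rate, so a feasibility problem can look like a favourable safety result. If testing completeness also differed between two strategies, their rate ratio would be distorted.

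**Working it through.** The plan gives no expected safety rate, event count or safety power, so there is no figure to reproduce. The check is direct arithmetic.

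**Inputs from the documents:** 12 scheduled sessions per period; a minimum of 6 attended; adherence of 90% (section VI) and at least 80% (Aim 1). Adherence also requires the dialysate adjustment, so POC completion is at least as high as adherence. The shortfalls at 90% and 80% are therefore upper limits when those targets are met.

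**Assumption:** event risk is the same at tested and untested sessions.

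**Formula.** With A sessions attended out of 12 and a share c of them tested, (rate per unit time) / (rate per tested session, on the same scale) = A × c / 12. The understatement is 1 − A × c / 12.

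| Attended | POC completion | Tested | Understatement |
|---|---|---|---|
| 12 | 90% | 10.8 | 10% |
| 12 | 80% | 9.6 | 20% |
| 9 | 100% | 9.0 | 25% |
| 9 | 80% | 7.2 | 40% |
| 6 | 100% | 6.0 | 50% |
| 6 | 80% | 4.8 | 60% |

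**Adding one standard-of-care lab per period**, drawn at an attended session regardless of POC completion, gives A × c + (1 − c) tested sessions. For 12 attended and 80% completion: 9.6 + 0.2 = 9.8, and 1 − 9.8/12 = 18% instead of 20%. For 90%: 10.8 + 0.1 = 10.9, so 9% instead of 10%. Across the cases in the table, the lab changes the result by 0 to 2 points.

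**Scale.** At an assumed 5% risk per session, full testing gives 12 × 0.05 = 0.60 events per patient-month. The time-based rate would be 0.60 × 0.90 = 0.54 or 0.60 × 0.80 = 0.48.

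**Comparison of strategies.** The observed ratio is the true ratio × (share tested under one strategy / share tested under the other). With equal completeness the ratio is unchanged. With a true ratio of 1.00 and 90% versus 80% tested, it is 0.90/0.80 = 1.125; the other way round, 0.80/0.90 = 0.89.

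**Holds triggered by a severe value.** This part needs a further assumption, that no test is done during the hold. A simulation with 12 sessions and assumed per-session risks of 10% versus 5% (true ratio 2.0) gave time-based ratios of about 1.90, 1.79 and 1.69 for holds of 1, 3 and 6 sessions. The ratio per tested session stayed at about 2.0.

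**The case against.** Much of the case against stands, and it limits the point.

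- A reader might infer that severe values can be seen only at a POC test. That is wrong: standard-of-care potassium and bicarbonate values are recorded too, and the anemia hold itself relies on monthly labs. They add little, as the arithmetic shows.
- A reader might infer that the plan explicitly counts missed or on-hold time as event-free. It does not. That follows from reading follow-up time literally; the term is undefined.
- Understatement is not certain. The Background describes electrolytes accumulating between sessions, so a missed session may make the next tested value more extreme. For the same reason a per-test rate is not neutral, and it should not replace the person-time rate.
- Larger figures are tempting. Including baseline and washout weeks would give 16 tested weeks of 23, a further 30%; but rates are to be compared between interventions, and those weeks belong to none. The 6-of-12 floor is a tolerated extreme, not an expectation. The hold results depend on invented risks and durations, and section VII says that patients come off therapy, not that testing stops.
- In a crossover each patient is their own control, so stable attendance habits largely cancel. Nothing in the documents suggests that completeness differs by strategy.
- The consequence is modest. Analyses are exploratory, Aim 1 sets no numeric threshold for minimal, and adherence will be reported for each intervention. At an assumed 5% risk, 20 patients × 12 sessions give 12 expected events per strategy. The exact Poisson 95% interval for 12 events is about 6.2 to 21.0 (−48% to +75%), before any allowance for clustering.

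None of this removes the core. Wide uncertainty does not justify a denominator whose error has a predictable link to testing failure. Adherence also mixes testing with dialysate adjustment, so it does not directly give the number of tests behind each rate.

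**Conclusion.** The concern holds for one component only, Study A's severe potassium and bicarbonate values. Followed as written, the plan lets that rate fall with the share of scheduled sessions tested. Given similar risk at untested sessions and full attendance, the shortfall is up to about 10% at 90% POC completion and up to about 20% at 80%. Missed sessions increase it, to 50% at the 6-of-12 extreme even if every attended session is tested.

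The strategy comparison is biased only if testing completeness differs between strategies. Attenuation from event-triggered holds is possible but rests on testing stopping during the hold, which the documents do not say. Serious adverse events, unscheduled dialysis and hospitalization are not affected. This is a cheap improvement, not a threat to the trial's conclusions.

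**What to change.** Amend the Safety paragraph in section VI and the matching Statistical Methodology text in the Study Summary:

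1. For severe potassium and bicarbonate values, report events per 100 completed tests in the intervention period. Compare strategies by Poisson regression with log(completed tests) as the offset. Show this beside the person-time rate.
2. State that the count covers intervention-period measurements, and use the same set of measurements in numerator and denominator.
3. State whether consecutive severe values count as one event or several.
4. Keep follow-up time as the denominator for serious adverse events, unscheduled dialysis and hospitalization.
5. Report completed tests per patient-period by strategy.

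The change is one of analysis wording. POC results are saved on the device and test completion is already assessed for adherence, so no new data are needed and patient care does not change. The price is a second denominator for one component of the endpoint and a slightly less favourable laboratory rate.

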## **V. Description of Study Procedures**

Two related, randomized cross-over trials will be performed; Study A-a dialysate interventions trial, consisting of 2 dialysate potassium interventions and 2 dialysate bicarbonate interventions (4 total cross-over interventions); and Study B- an ultrafiltration rate intervention trial, consisting of 2 separate ultrafiltration rate strategies. A total of 20 patients will be enrolled in each trial. An overview of the study design is illustrated in **Figure 5 below**.

**ILR Intervention**— Consent and ILR placement at the local site will be followed by a one-month baseline observation period. ILR placement will be followed by wound check visits at 1 week and 1-month post implant. Outpatient insertion of ILR by study cardiologists will occur within 4 weeks of enrollment. Reveal LINQ™ (Medtronic) implantable monitors will be utilized.

**Arrhythmia Detection**—Detection of clinically significant arrhythmias (CSA) will be achieved using implantable loop monitors (ILR) inserted at the start of each trial. ILR tracings will be batch analyzed by study cardiologists blinded to randomized treatment. Tracings from ILR-detected events meeting automated, validated detection criteria for bradycardia, asystole, AF, sustained or non-sustained ventricular tachycardia (VT) will be manually reviewed at least once every two weeks. Clinically significant arrhythmias will be defined on the basis of arrhythmias likely to lead to sudden cardiac arrest or serious morbidity and mortality and will include atrial fibrillation (AF), asystole lasting  $\geq 3$  seconds, bradycardia  $\leq 40$  beats per minute lasting  $\geq 6$  seconds, sustained VT  $\geq 130$  beats per minute lasting  $\geq 30$  seconds, and any sudden cardiac arrest. Positively adjudicated CSA will be entered into a study database and coded according to arrhythmia type, date and duration.

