**Dialysate Interventions Trial (Study A)**—This trial will test the impact of dialysate K and HCO3 on CSA. After a month of usual care, subjects will cross-over in random order to four month-long periods using alternative approaches to algorithm-specified manipulation of dialysate K or HCO3 guided by POC-obtained laboratory testing prior to each dialysis. There will be a one-week washout with usual care between each intervention period. Randomization sequences will be balanced with respect to treatments to minimize impact of sequence or carryover effects on outcomes. Algorithms tested will compare **a) Minimization of dialysate-serum potassium gradient vs. maximization of potassium removal** (preferential use of high potassium dialysate to minimize gradient vs. low K dialysate to maximize removal); and **b) Alkalosis avoidance vs. acidosis avoidance** (preferential use of lower dialysate HCO3 concentration vs. higher dialysate HCO3). Subjects and investigators will be blinded to the intervention in use. HD nurses and staff will obtain POC chemistry results prior to each HD session and adjust the prescription for dialysate potassium or HCO3 as dictated by the algorithm. Since dialysate prescription changes must be entered manually, dialysis staff cannot be blinded to the algorithms, but they will not assess endpoints or be otherwise involved in interpretation of study data.

Whole blood (100  $\mu$ L) will be obtained by dialysis staff when the catheter, fistula or graft is accessed prior to each HD session during the K and HCO3 intervention periods. Blood will be drawn into a non-heparinized syringe and added to the i-STAT cartridge for immediate testing—a process similar to routine blood glucose testing during HD. Blood will be immediately tested on the i-STAT according to the manufacturer's protocol. (Alternatively blood may be drawn into heparinized tubes, mixed by inversion, and tested within 10 minutes). Results are saved on the device, printed, and can be entered directly to the study data-base.

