After ILR placement, subjects will crossover between two UF rate interventions: 1) UF rate-restricted dialysis, in which UF rates are limited to a maximum of 10 mL/kg/hr for the duration of the session 2) UF rate-unrestricted dialysis. It is anticipated that patients with large interdialytic weight gains in the UF rate-restricted intervention may not achieve their target post-dialysis weight during the prescribed treatment time. In order to prevent progressive volume overload and the need for additional HD sessions to manage volume gains in this scenario, subjects will crossover weekly between the restricted

and unrestricted UF interventions. This weekly crossover accomplishes two important goals: First, it reduces safety concerns by ensure that any volume gained due to limiting the UF are constrained to one week and promptly addressed with unlimited UF the following week. Second, it increases separation between UF rates in the two interventions, since a higher UF-rate will be needed to address any weight and volume gains resulting from UF-rate restriction.

Investigators will be blinded. Subjects will not be blinded as it is not feasible to blind them to the goal UF and post-dialysis weight (typically self-measured); HD staff will have access to the algorithm in order to adjust UF rate accordingly. Following a one-month baseline observation period with usual care, subjects will undergo 4 weeks of each UF intervention administered in alternating weeks as described above, for a total study duration of 12 weeks. Data will be aggregated and results compared using a full month of data for each intervention.

**End of Study Procedures**—In order to maximize recruitment efficiency and the significant investment in undergoing ILR implantation, patients completing one study will be given the option of continuing to eligibility screening and enrollment for the alternate study. If subjects consent to both Study A and Study B, then the baseline observation period for the second study may be less than 1 month. Those refusing or ineligible will be offered ILR explanation.

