**Safety Endpoints**—The primary safety endpoint will include the incidence of all serious adverse events and intervention-specific complications: a) Potassium Intervention—severe K abnormalities ( $K \geq 6.5$  or  $\leq 3.0$  mEq/L), or unscheduled HD or hospitalization for hyper/hypokalemia in the absence of a missed treatment; b) Bicarbonate Intervention—severe  $HCO_3$  abnormalities ( $HCO_3 < 20$  or  $> 32$  mEq/L) or unscheduled HD or hospitalization for acid base abnormalities in the absence of a missed treatment; c) Ultrafiltration Intervention—Unscheduled HD or hospitalization for volume overload. Secondary safety endpoints include the occurrence of CSAs requiring further management, all-cause mortality, cardiovascular mortality, and hospitalization.

**Recruitment Feasibility (Aim 2)**—Recruitment feasibility will be analyzed by testing whether an overall recruitment rate of 1 patient/month is achieved in each trial (1-sample test). This is a critical metric, as a large-scale trial cannot be feasibly completed in a practical number of centers if between 0.5-1 patient/month cannot be enrolled. This rate represents a minimum criterion for feasibility.

The percent of screened patients enrolled will be calculated as a secondary feasibility measure to assess the size of the necessary screening pool. Reasons for non-enrollment (vis-a-vis inclusion and exclusion criteria and patient and physician preferences) will be assessed to determine the potential for protocol modification to improve recruitment. Subject retention will be calculated as the percentage of enrolled patients completing the trial. Retention rates of 90% will be considered the benchmark for feasibility.

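### The safety Poisson model makes no allowance for repeat events in the same subject, so its standard errors may be too small or too large.

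*Combined protocol and SAP*

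**What the plan says.** Section VI (Biostatistical Analysis) defines the outcome broadly: "The primary safety endpoint will include the incidence of all serious adverse events and intervention-specific complications". The intervention-specific complications include severe potassium or bicarbonate values in Study A, and unscheduled dialysis or hospitalization for volume overload in Study B. The analysis begins by "calculating the incidence rate (complications per unit follow-up time) for serious adverse events and intervention-specific complications". That is a rate of events with no first-event-only rule, so repeats can count.

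The comparison is then specified: "Comparisons of incidence rate between interventions will utilize Poisson regression adjusted for randomization scheme and site". The Study Summary repeats this. The threshold is "P<0.05 will be considered significant in all safety analyses". The section adds: "Exploratory analyses will assess age, sex, race, mean intra-dialytic weight gain", together with baseline potassium and bicarbonate, but names no model for those predictors.

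The next paragraph of Section VI gives the efficacy model terms for period and sequence and random effects for subjects. The safety model has no counterpart. Randomization scheme may be meant to cover sequence or period, but it does not name the subject.

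On design, Section V says: "A total of 20 patients will be enrolled in each trial". In Study A, "subjects will cross-over in random order to four month-long periods"; in Study B, "subjects will undergo 4 weeks of each UF intervention administered in alternating weeks". Section VII says electrolytes are tested at every session, three times a week, which is about 12 tests in a four-week period.

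**The concern.** The same subjects supply several periods, and in Study A one subject can log the same complication at several sessions of a period. A bicarbonate below 20 mEq/L is the clearest route. It counts as a safety complication, Study A has no bicarbonate exclusion at entry, and the bicarbonate algorithm has its own row for values below 20. A plain Poisson model takes the variance of each count to equal its mean, given the covariates. If events arrive in bursts within a subject's period, the true variance is larger and the reported standard error is too small.

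Safety is part of Aim 1, and the trial's declared purpose is to inform definitive trials. Misstated standard errors would distort both the significance calls and the interval widths carried into that planning.

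**Working it through.** **No stated figure to reproduce.** The documents give no event rate, dispersion or power for the safety comparison. The check is whether a nominal 5% test keeps 5%.

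**Inputs from the documents:** 20 subjects per trial; two sites; balanced crossover; Poisson regression; threshold 0.05 (sidedness not stated, two-sided assumed); about 12 tested sessions per period; 90% retention benchmark.

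**Assumptions (not in the documents):** one pair of interventions with one period each; mean μ = 0.3, 1 or 3 events per subject-period; between-subject gamma variance v from 0 to 2; subject-by-period gamma variance w from 0 to 1.

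**Treatment contrast.** Given subject risk f (mean 1, variance v), the within-subject difference between two period counts has variance 2μf + 2μ²f²w. Averaging over subjects, with E(f²) = 1 + v, gives 2μ[1 + μw(1 + v)]. The Poisson model assumes 2μ. The variance inflation is therefore

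k = 1 + μw(1 + v), with type I error ≈ 2[1 − Φ(1.96/√k)].

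If w = 0, then k = 1 whatever v is: stable subject differences cancel. If events are capped at one per session over 12 sessions and w = 0, then k = 1 − μ(1 + v)/12, which is below 1.

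The approximation is set beside a simulation of 3,000 null trials per scenario (plain Poisson with treatment, site, sequence and exposure offset):

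| Scenario | μ, v, w | k | Approx. error | Simulated error |
|---|---|---|---|---|
| Stable risk only | 1, 1, 0 | 1 | 5% | 4.2% |
| Within-period clustering | 1, 1, 0.5 | 2 | 17% | 15.1% |
| Within-period clustering | 1, 1, 1 | 3 | 26% | 21.9% |
| Within-period clustering | 3, 1, 0.5 | 4 | 33% | 31.4% |
| Within-period clustering | 3, 1, 1 | 7 | 46% | 43.3% |
| Rare events, clustered | 0.3, 1, 1 | 1.6 | 12% | 7.2% |
| Capped at 12 sessions | 1, 2, 0 | 0.75 | 2.4% | 2.9% |
| Capped at 12 sessions | 3, 1, 0 | 0.5 | 0.6% | 0.9% |

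In the worst case (3, 1, 1) the mean reported standard error was 0.197 against an actual standard deviation of 0.490. In the second capped case it was 0.188 against 0.143.

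Other results from the same simulation:
- Capped events with within-period clustering (μ = 3, v = 1, w = 0.5 to 1): 16% to 26%.
- Stable risk only (v = 2, w = 0) with 10% of subjects missing the second period: 5.5% at μ = 1 and 7.8% at μ = 3.

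**Patient-level predictors.** Here v does not cancel. With m = mean total events per subject and stable risk only, the inflation is 1 + vm. For v = 1:
- m = 0.6: 1.6, error about 12%.
- m = 2: 3, error about 26%.
- m = 4: 5, error about 38%.

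A simulation over a range of assumed rates and variances gave 10% to 51%. One row per subject would not cure this, because the excess variance lies between subjects.

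**With subject-clustered variance and a t reference on 19 df**, the treatment test rejected between about 4% and 10% of the time across the scenarios. The worst case fell from 43.3% to 9.8%. Predictor tests rejected about 8–11% of the time.

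**The case against.** A reader might infer something stronger: that repeated measurement across periods by itself makes the safety standard errors and significance calls wrong. The documents do not support that. The design is a balanced, uniform crossover, and the stable-risk row shows the plain test holding its level. Error can also run the other way when events are capped by session.

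The large figures need event rates the documents do not give, and the plan expects few events. Aim 1 hypothesises that severe abnormalities will be minimal, the stopping-rules text in Section IX refers to a low likelihood of significant events, and Study A excludes recent potassium above 6.5 or below 3.5. Section VII also takes subjects with severe potassium or bicarbonate values temporarily off therapy, at limits close to those of the endpoint, which may curb repeats. In Study B the specific complications are unscheduled dialysis or hospitalization, so the argument from repeated session tests does not apply. All of this stands, and it is why the low end of the range is as plausible as the high end. It does not settle the matter, because no rule says whether off-therapy time or later events count.

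Two further inferences go beyond the text. The plan does not say that the exploratory predictors use Poisson regression, nor that these P values reach the DSMB, whose event reviews rest on narratives and which has no formal stopping rules.

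Finally, Section VI calls the analyses exploratory and conservatively interpreted. That lowers the stakes and excuses the lack of multiplicity adjustment. It does not supply a valid standard error where significance is still declared at 0.05.

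**Conclusion.** The point holds in a limited form. The plan states a concrete safety model for events that can repeat in about 20 crossover subjects and gives it no protection against within-subject clustering. The consequence is possible miscalibration in either direction, not a demonstrated error.

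For the nominal 5% treatment test, expect roughly 1–8% when events are rare, capped by session, or vary only with stable subject risk. Expect about 15–40% at 1–3 events per subject-period with within-period clustering. Patient-level predictor tests, if run with the same model, would reject about 10–50% of the time. All of these sizes rest on assumed event rates and gamma variances. The omission is certain from the text; its size is not. It should be corrected before analysis, but it does not threaten the trial's feasibility aims.

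**What to change.** In Section VI, and in the matching line of the Study Summary:

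- Make the subject-period count the unit of analysis, with log follow-up time or log monitored sessions as offset and terms for treatment, period, sequence and site.
- Use subject-clustered robust variance with a small-sample correction. A within-subject permutation test is an alternative for treatment.
- If a random subject effect is preferred, add a dispersion term. A random intercept alone does not absorb clustering within a period.
- Name the model for the exploratory patient-level predictors and apply the clustered variance there too.
- State how repeat events, and time off therapy under the Section VII rule, enter the numerator and the exposure. In doing so, reconcile that rule with the bicarbonate algorithm's row for values below 20.

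The cost is SAP wording and a little more analysis work. Intervals may widen or narrow. With about 20 clusters the error rates stay approximate: about 4–11% in simulation before a small-sample correction.
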